6.4.2 Secondary Efficacy Endpoints

The secondary endpoints are change in CDR-SB and MMSE scores from baseline to the last visit of the double-blind treatment period (Week 49 for Cohort 1 *or* Week 61 for Cohort 2). Secondary efficacy endpoints will be analyzed in the same manner as the primary endpoint.

6.5 SAFETY ANALYSES

The safety analysis population will consist of all randomized patients who received at least one dose of either MTAU9937A or placebo, or GTP1, with patients grouped according to treatment arm. Patients will be analyzed according to actual MTAU9937A treatment received.

All adverse events that occur after informed consent is given will be summarized by mapped term, appropriate thesaurus level, and toxicity grade. In addition, all serious adverse events, including deaths and events leading to discontinuation, will be listed separately and summarized.

Laboratory data will be summarized by descriptive statistics by treatment group. In addition, all laboratory abnormalities will be summarized by grade using the WHO grading scale.

Adverse events of special interest and neuroimaging abnormalities will be listed and summarized by treatment group.

Vital signs (pulse rate, blood pressure, body temperature, and respiratory rate), weight, and other disease-specific data will be summarized by descriptive statistics by treatment group. Changes from baseline will be summarized by treatment group.

Detailed statistical methods will be outlined in the Data Analysis Plan.

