3. STUDY DESIGN

3.1 DESCRIPTION OF THE STUDY

3.1.1 Overview of Study Design and Study Treatment

This Phase II, multicenter, randomized, double-blind, placebo-controlled, parallel-group study will evaluate the clinical efficacy, safety, pharmacokinetics, and pharmacodynamics of MTAU9937A in patients with moderate AD.

The study consists of a screening period, a double-blind treatment period, an optional open-label extension (OLE) period, and a safety follow-up period (see [Figure 1](#) for the study schema and [Appendix 1–Appendix 4](#) for the schedules of activities). An extended baseline visit (up to 15 days) is included in the double-blind treatment period, following randomization and prior to the initiation of study drug. Study drug (MTAU9937A or placebo) will be administered intravenously in the double-blind treatment period, and MTAU9937A will be administered intravenously in the optional OLE period. Study drug administration will occur every 2 weeks (Q2W) for the first three doses of the double-blind treatment period and every 4 weeks (Q4W) thereafter during the double-blind treatment period. Because of anticipated disruptions in study drug administration associated with the global COVID-19 pandemic, there may be up to *two* study cohorts, as described below:

- Cohort 1: Patients who had completed or discontinued from the double-blind treatment period (i.e., completed Week 49 assessments) prior to implementation of Protocol Version 3. For Cohort 1, the Week 49 visit represents the end of the double-blind treatment period and patients will continue into the OLE or safety follow-up periods per the original schedule (see [Appendix 2](#)). In addition, patients in other cohorts who are active in the double-blind treatment period and have completed blinded study drug treatment through Week 45 without any missed doses will be eligible to revert to the Cohort 1 Schedule of Activities (see [Appendix 1](#)) at the Week 49 visit and continue to the OLE (see [Appendix 2](#)) after completing the Week 49 visit assessments.

If a Cohort 1 patient misses any blinded study drug infusion, the patient will be moved into Cohort 2.

- Cohort 2: Patients who were active in the double-blind treatment period after implementation of Protocol Version 3 were assigned to Cohort 2. In Cohort 2, the double-blind treatment period is extended to Week 61, unless the criteria above for reverting to the Cohort 1 Schedule of Activities are fulfilled.

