6. STATISTICAL CONSIDERATIONS AND ANALYSIS PLAN

The efficacy analyses will be based on the modified intent-to-treat population, which is defined as all randomized patients who receive at least one dose of study drug and have at least one postbaseline ADAS-Cog11 and/or ADCS-ADL measurement. For the efficacy analysis, patients will be grouped according to the treatment assigned at randomization.

The safety analysis will be based on all randomized patients who receive at least one dose of either MTAU9937A or placebo. Patients will be grouped according to MTAU9937A treatment actually received.

- A primary analysis will occur after the last patient has completed the assessments for the last visit of the double-blind treatment period (Week 49 for Cohort 1 *or* Week 61 for Cohort 2).
- A final analysis will occur after the last patient has completed the OLE and completed the assessments for the last visit of the OLE period (Week 145 for Cohort 1 *or* Week 157 for Cohort 2).

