Appendix 1: Cohort 1 Schedule of Activities

- c The baseline visit period must begin after enrollment (randomization) and may be split over multiple visit days; the first and last visit days of the baseline period must be separated by no more than 14 days from each other (e.g., the baseline visit period may start on a Monday and end on the Monday 2 weeks later). All COA assessments during the baseline visit period should be performed as close to the last visit day of the baseline period as possible. COA assessments, [¹⁸F]GTP1 PET scan, and LP from the baseline visit period may be performed on the same day that study drug is first administered (on the Week 1 visit), but they must be performed prior to dosing. All activities specified for the Week 1 visit (the first dosing visit) must be performed on the same day and must occur no later than 15 days after the baseline visit period begins (e.g., if the first baseline visit period day is a Monday, then the first dosing of study drug must occur no later than the Tuesday 2 weeks later). Extensions to the 15-day baseline visit period (e.g., to complete [¹⁸F]GTP1 PET imaging) may be granted on a case-by-case basis by the Medical Monitor.
- d At this visit, all activities/assessments must be performed within ± 3 days of the scheduled visit.
- e At Week 49, patients will move to OLE or will be scheduled for a treatment completion visit (safety follow-up).
- f Informed consent must be documented before any study-specific screening procedure is performed. Informed consent with the Early Screening Informed Consent Form permits MMSE, medical history, AD history, personal status, and demographics. Informed consent with the main Informed Consent Form is required for all other study-specific screening procedures.

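### Sections 6 and 6.5 state two different safety populations, one admitting patients who had only a GTP1 scan, and the general adverse event summary starts at consent (small effect, possibly zero)

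*Combined protocol and SAP*

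**What the plan says.** Section 6 states: "The safety analysis will be based on all randomized patients who receive at least one dose of either MTAU9937A or placebo". It adds: "Patients will be grouped according to MTAU9937A treatment actually received".

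Section 6.5 gives the population as "all randomized patients who received at least one dose of either MTAU9937A or placebo, or GTP1, with patients grouped according to treatment arm", and then says: "Patients will be analyzed according to actual MTAU9937A treatment received". On adverse events it says "All adverse events that occur after informed consent is given will be summarized by mapped term", followed by thesaurus level and toxicity grade. It closes with: "Detailed statistical methods will be outlined in the Data Analysis Plan". That plan is not among the documents.

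On timing, Section 3.1.1 places the extended baseline visit "following randomization and prior to the initiation of study drug". Appendix 1, footnote c, says: "The baseline visit period must begin after enrollment (randomization) and may be split over multiple visit days". The same footnote lets the GTP1 scan fall on the day of the first infusion, provided it comes before dosing. Appendix 3 repeats this for Cohort 2.

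Section 5.3.1 sets what is collected. Before any study drug or radioligand, only serious events caused by a protocol procedure are reported. After the first study drug, GTP1 or amyloid radioligand, all adverse events are reported.

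**The concern.** Both definitions are in the current text, and both cannot be the safety denominator. The patients on whom they differ (randomised, scanned with GTP1, never infused) have no value for the variable that Section 6.5 uses to form groups. Whoever programs the tables would have to choose between the randomised arm, the placebo column and exclusion.

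The event rule raises a second, related question. Section 2.2 makes the comparison of MTAU9937A with placebo the safety objective. An event that starts before the first infusion carries no information on that comparison, yet Section 6.5's general summary starts at consent and has no treatment-emergent restriction. Elsewhere the protocol does draw the line: Section 5.1.1.2 counts MRI abnormalities as events of special interest only after study drug has been received.

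At stake are the denominator and the event count in the descriptive safety tables. Efficacy, sample size and the significance level are untouched.

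**Working it through.** The plan gives no figure on this point, so there is none to reproduce. The check sets the texts side by side and then bounds the size.

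**1. Can a GTP1-only patient exist?** The order is randomisation, then the baseline period (which contains the GTP1 scan), then the first infusion. A patient who leaves between the scan and the infusion is outside the Section 6 population and inside the Section 6.5 population. The answer is yes.

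**2. Which group would that patient join?** The first sentence of Section 6.5 points to the treatment arm. The second points to MTAU9937A treatment actually received, which is also the Section 6 rule. For dosed patients the second sentence settles the matter. For a never-dosed patient it gives no answer.

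**3. How many such patients?** The documents give no count for this study. The only proxy is Study GN39763 (Section 1.2.2), with 457 randomised and 441 dosed.

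- Never dosed: 457 − 441 = 16, and 16/457 = 3.50%.
- Exact (Clopper-Pearson) 95% interval, from the 2.5% quantile of Beta(16, 442) and the 97.5% quantile of Beta(17, 441): 2.01% to 5.62%.
- Applied to 260 patients: 9.1 (5.2 to 14.6).

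This is a ceiling under the assumed share, because every never-dosed patient must also have been scanned. Section 1.3 reports a baseline GTP1 scan in 399 GN39763 patients. The number randomised but not scanned was 457 − 399 = 58, which is large enough to contain all 16. The lower end is therefore 0.

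**4. What would they do to an incidence?** Nothing, if they are left out of both columns. If they are counted in the arms, event-free, with m such patients:

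- Split evenly, an incidence is multiplied by (260 − m)/260. An illustrative 20% reads 19.3% at m = 9.1 (19.6% at 5.2, 18.9% at 14.6). A 10-point difference reads 9.65 (9.80 to 9.44). The risk ratio does not change.
- All placed in the placebo column, with m = 9 and 130 − 4.5 = 125.5 dosed per arm, an illustrative 30% reads 30 × 125.5/134.5 = 28.0%. Split by arm it reads 29.0%.

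**5. What would pre-dose events do?** Assume constant event rates, twice as high on drug as on placebo, and the placebo rate in both arms before the first infusion. Take every scan on day 1 of the standard 15-day window, so p = 15/7 = 2.14 weeks. Follow-up T is 48 weeks (Cohort 1) or 60 weeks (Cohort 2).

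- Rate ratio: (2T + p)/(T + p) = 98.14/50.14 = 1.957, or 122.14/62.14 = 1.966, against a true 2.0.
- Incidence: take placebo at 20% over T. Drug is then 1 − 0.8² = 36%, a 16.0-point difference. With q = 0.8^(p/T), placebo reads 1 − 0.80q and drug 1 − 0.64q, so the difference is 0.16q.
- T = 48: q = 0.990, giving 20.8% vs 36.6%, a difference of 15.84 points.
- T = 60: q = 0.992, giving 20.6% vs 36.5%, a difference of 15.87 points.

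A scan nearer the infusion, or a longer follow-up window, makes this smaller. A screening amyloid PET or an extended baseline period lengthens the pre-dose window. The documents do not fix that length, so it is not quantified.

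**The case against.** The case for leaving the text alone has real substance.

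- **GTP1 has a reason to be there.** It is a named test product, is not approved (Section 5.1) and is part of study treatment (Section 3.1.1). A population covering exposure to either product makes sense for radioligand safety. This stands, and it supports a separate radioligand table. It does not support a second denominator for the drug-placebo comparison.
- **A reader might infer that Section 6.5 dilutes every drug-placebo incidence**, so that 20% becomes 19.3%. The documents do not support that. It would require never-dosed patients to be counted in both arms, against Section 6.5's own actual-treatment rule, and all of them to have been scanned.
- **A reader might infer that the drug-placebo adverse event comparison itself runs from consent.** The sentence does not go that far. Unlike the sentences on laboratory data, events of special interest and vital signs, it does not say the summary is by treatment group, and it does not rule out a treatment-emergent table. MRI events of special interest are already defined as treatment-emergent (Section 5.2.3). What stands is that the one general summary described includes pre-dose events and that no restricted one is promised.
- **Detail is deferred to the Data Analysis Plan.** That plan may well define the event window, so its absence here cannot be called an omission. Deferral does not, however, reconcile two explicit population definitions that disagree.

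**Conclusion.** The inconsistency is certain and minor. Sections 6 and 6.5 name different safety populations, and patients who received only GTP1 fall in one of them with no comparison group. Events before the first infusion enter the general adverse event summary, where they cannot inform MTAU9937A versus placebo.

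The effect lies between nothing and very little. On the never-dosed side the ceiling is about 9 of 260 patients (5 to 15). That assumes the GN39763 share carries over and that all such patients were scanned, and it changes incidences only if they are counted in the arms. On the pre-dose side, an illustrative 16.0-point difference falls no lower than about 15.8 under the standard 15-day window and the assumed rates. The event rates are illustrations and do not come from the documents.

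The point does not show a biased safety comparison, and it has no bearing on efficacy or power.

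**What to change.** Change the wording in Sections 6 and 6.5 only:

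1. Use the Section 6 definition in both places for drug-placebo tables: randomised, at least one dose of MTAU9937A or placebo, grouped by treatment actually received.
2. Base those tables on events with onset on or after the first dose of MTAU9937A or placebo. Name the products, because Section 5.3.1 at one point brackets the radioligands with study drug.
3. Report separately the pre-dose events and the radioligand events. The radioligand table covers all scanned patients, including those never dosed, and the 4-day causality window in Section 5.3.4 is its natural limit.
4. As a clarification only, confirm in the Data Analysis Plan where the double-blind event window ends and how open-label events are handled.

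Section 5.1.1.2 says that unblinded safety data from this study have already been examined, so record the change as made after unblinding. The population adopted is one the protocol already states. The cost is a text edit and the corresponding table specifications, with no new data, visits or delay.

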2.2 SAFETY OBJECTIVES

The safety objectives for this study are to evaluate the safety and tolerability of MTAU9937A compared with placebo on the basis of the following endpoints:

- Nature, frequency, severity, and timing of adverse events and serious adverse events, with severity determined according to WHO toxicity grading scale
- Changes from baseline in vital signs, physical findings, neurologic findings, ECG, and clinical laboratory results during and following MTAU9937A administration
- Changes from baseline in suicidal ideation and behavior during and following MTAU9937A administration as assessed by the Columbia-Suicide Severity Rating Scale (C-SSRS)
- Nature, frequency, severity, and timing of neuroimaging abnormalities that could represent cerebral vasogenic edema and/or microhemorrhage, during MTAU9937A administration

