5.3.3 Assessment of Severity of Adverse Events

The WHO toxicity grading scale (see [Appendix 7](#)) will be used for assessing adverse event severity. [Table 3](#) will be used for assessing severity for adverse events that are not specifically listed in the WHO toxicity grading scale.

Table 3 Adverse Event Severity Grading Scale for Events Not Specifically Listed in WHO Toxicity Grading Scale

Grade	Severity
1	Mild; transient or mild discomfort (<48 hours); no medical intervention or therapy require
2	Moderate; mild to moderate limitation in activity; some assistance may be needed; no or minimal medical intervention or therapy required
3	Severe; marked limitation in activity; some assistance usually required; medical intervention or therapy required; hospitalization possible
4	Life-threatening; extreme limitation in activity; significant assistance required; significant medical intervention or therapy required, hospitalization or hospice care probable

Notes: Developed by the Division of Microbiology and Infectious Diseases.

Regardless of severity, some events may also meet seriousness criteria. Refer to definition of a serious adverse event (see Section 5.2.2).

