Appendix 6 **Anaphylaxis Precautions**

The following equipment is needed in the event of a suspected anaphylactic reaction during study drug infusion:

- Monitoring devices: ECG monitor, blood pressure monitor, oxygen saturation monitor, and thermometer
- Oxygen
- Epinephrine for intravenous, intramuscular, and endotracheal administration in accordance with institutional guidelines
- Antihistamines
- Corticosteroids
- Intravenous infusion solutions, tubing, catheters, and tape

The following are the procedures to follow in the event of a suspected anaphylactic reaction during study drug infusion:

- Stop the study drug infusion.
- Call for additional medical assistance.
- Maintain an adequate airway.
- Ensure that appropriate monitoring is in place, with continuous ECG and pulse oximetry monitoring, if possible.
- Administer antihistamines, epinephrine, or other medications as required by participant status and as directed by the physician in charge.
- Continue to observe the participant and document observations.
- Draw serum samples for immunogenicity testing.
- Ask participant to return for washout immunogenicity sample (12 weeks after last dose) if appropriate.

Appendix 7
World Health Organization Toxicity Grading Scale for
Determining Severity of Adverse Events

HEMATOLOGY				
ITEM	Grade 1 Toxicity	Grade 2 Toxicity	Grade 3 Toxicity	Grade 4 Toxicity
Hemoglobin	9.5 - 10.5 gm/Dl	8.0 - 9.4 gm/Dl	6.5 - 7.9 gm/Dl	< 6.5 gm/Dl
Absolute Neutrophil Count	1000-1500/mm ³	750-999/mm ³	500-749/mm ³	<500/mm ³
Platelets	75000-99000/mm ³	50000-74999/mm ³	20000-49000/mm ³	<20000/mm ³
Prothrombin Time (PT)	1.01 - 1.25 x ULN	1.26-1.5 x ULN	1.51 -3.0 x ULN	>3 x ULN
Activated Partial Thromboplastin (APPT)	1.01 -1.66 x ULN	1.67 - 2.33 x ULN	2.34 - 3 x ULN	> 3 x ULN
Fibrinogen	0.75 - 0.99 X LLN	0.50 - 0.74 x LLN	0.25 - 0.49 x LLN	< 0.25 x LLN
Fibrin Split Product	20-40 mcg/ml	41-50 mcg/ml	51-60 mcg/ml	> 60 mcg/ml
Methemoglobin	5 - 9.9 %	10.0 - 14.9 %	15.0 - 19.9%	> 20 %
LIVER ENZYMES				
AST (SGOT)	1.25 - 2.5 x ULN	2.6 - 5 x ULN	5.1 - 10 x ULN	> 10 x ULN
ALT (SGPT)	1.25 - 2.5 x ULN	2.6 - 5 x ULN	5.1 - 10 x ULN	> 10 x ULN
GGT	1.25 -2.5 x ULN	1.6 - 5 x ULN	5.1 - 10 x ULN	> 10 x ULN
Alkaline Phosphatase	1.25 - 2. 5 x ULN	1.6 - 5 x ULN	5.1 - 10 x ULN	> 10 x ULN
Amylase	1.1 - 1.5 x ULN	1.6 - 2.0 x ULN	2.1 - 5.0 x ULN	> 5.1 x ULN
CHEMISTRIES				
Hyponatremia	130-135 mEq/L	123-129 mEq/L	116-122 mEq/L	< 116 or mental status changes or seizures

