Hemorrhage, Blood Loss	microscopic/occult	mild, no transfusion	gross blood loss; 1-2 units transfused	massive blood loss; > 3 units transfused

Appendix 7: World Health Organization Toxicity Grading Scale for Determining Severity of Adverse Events

RESPIRATORY				
Cough	transient- no Rx	treatment associated cough local Rx	uncontrolled	
Bronchospasm, Acute	transient; no Rx < 80% - 70% FEV ₁ (or peak flow)	requires Rx normalizes with bronchodilator; FEV ₁ 25% - 50% (or peak flow retractions)	no normalization with bronchodilator; FEV ₁ 25% - 50% (or peak flow retractions)	cyanosis: FEV ₁ < 25% (or peak flow) or intubated
GASTROINTESTINAL				
Stomatitis	mild discomfort; no limits on activity	some limits on eating/drinking	eating/talking very limited	requires IV fluids
Nausea	mild discomfort; maintains reasonable intake	moderate discomfort; intake decreased significantly; some activity limited	severe discomfort; no significant intake; activities limited	minimal fluid intake
Vomiting	transient emesis	occasional/moderate vomiting	orthostatic hypotension or IV fluids required	hypotensive shock or hospitalization required for IV fluid therapy
Constipation	mild	moderate	severe	distensions w/vomiting
Diarrhea	transient 3-4 loose stools/day	5-7 loose stools/day	orthostatic hypotension or > 7 loose stools/day or required IV fluids	hypotensive shock or hospitalization for IV fluid therapy required
NEURO & NEUROMUSCULAR				
Neuro-Cerebellar	slight incoordination dysdiadochokinesis	intention tremor, dysmetria, slurred speech; nystagmus	locomotor ataxia	incapacitated
Mood	mild anxiety or depression	moderate anxiety or depression and therapy required	severe anxiety or depression or mania; needs assistance	acute psychosis; incapacitated, requires hospitalization
Neuro Control (ADL = activities of daily living)	mild difficulty concentrating; no Rx; mild confusion/agitation; ADL unaffected	moderate confusion/agitation some limitation of ADL; minimal Rx	severe confusion/agitation needs assistance for ADL; therapy required	toxic psychosis; hospitalization
Muscle Strength	subjective weakness no objective symptoms/ signs	mild objective signs/symptoms no decrease in function	objective weakness function limited	paralysis

Appendix 7: World Health Organization Toxicity Grading Scale for Determining Severity of Adverse Events

OTHER PARAMETERS				
Fever: oral, > 12 hours	37.7 - 38.5 C or 100.0 - 101.5 F	38.6 - 39.5 C or 101.6 - 102.9 F	39.6 - 40.5 C or 103 - 105 F	> 40 C or > 105 F

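### Appendix 7 gives two grades to GGT and alkaline phosphatase values of 1.6–2.5 × ULN and to fever above 40.0 and up to 40.5 °C, and the protocol has no rule for choosing between them

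*Combined protocol and SAP*

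**What the plan says.** Section 2.2 defines the adverse event endpoint "with severity determined according to WHO toxicity grading scale". Section 6.5 says that adverse events "will be summarized by mapped term, appropriate thesaurus level, and toxicity grade" and that "all laboratory abnormalities will be summarized by grade using the WHO grading scale". The scale itself is Appendix 7. Section 5.3.3 supplies a fallback, Table 3, but it "will be used for assessing severity for adverse events that are not specifically listed in the WHO toxicity grading scale", so it does not reach items that Appendix 7 lists.

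The rows in question, Grade 1 then Grade 2:
- "GGT 1.25 -2.5 x ULN 1.6 - 5 x ULN"
- "Alkaline Phosphatase 1.25 - 2. 5 x ULN 1.6 - 5 x ULN"

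For contrast, a row from the same block:
- "AST (SGOT) 1.25 - 2.5 x ULN 2.6 - 5 x ULN"

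For fever (oral, lasting more than 12 hours), Grade 3 is "39.6 - 40.5 C or 103 - 105 F". The Grade 4 cell is above 40 °C or above 105 °F.

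Neither Section 5.3.3 nor Section 6.5 says what to do with a value that satisfies two grades.

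**The concern.** A grading table has to send each value to one grade. Here two laboratory rows and one clinical row do not.

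GGT and alkaline phosphatase are both in the scheduled central chemistry panel (Section 4.5.9), so their rows will be applied repeatedly. The split between Grade 1 and Grade 2 in the tables required by Section 6.5 then depends on a choice that the protocol does not make.

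Fever is graded by the investigator as part of each adverse event record (Section 5.3). The choice between Grade 3 and Grade 4 can therefore differ between sites, and can depend on whether the temperature was read in Celsius or Fahrenheit. At stake is the reproducibility of descriptive severity tables.

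**Working it through.** The protocol states no figure to reproduce. The check is whether the printed bands are disjoint. All limits are from Appendix 7.

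**GGT and alkaline phosphatase (× ULN)**
- Grade 1 is 1.25 to 2.5. Grade 2 is 1.6 to 5.
- Intersection: from max(1.25, 1.6) = 1.6 to min(2.5, 5) = 2.5.
- Share of the Grade 1 band: (2.5 − 1.6) / (2.5 − 1.25) = 0.9 / 1.25 = 72%.
- Share of the Grade 2 band: 0.9 / (5 − 1.6) = 0.9 / 3.4 = 26%.
- AST and ALT: Grade 1 ends at 2.5 and Grade 2 starts at 2.6, so there is no overlap.

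**Which limit is wrong?** The appendix points both ways.
- AST and ALT share the 1.25–2.5 Grade 1 band and start Grade 2 at 2.6. On that pattern, every value from 1.6 to 2.5 is Grade 1.
- Amylase, hyperbilirubinemia and creatinine start Grade 2 at 1.6, after a Grade 1 ceiling of 1.5. On that pattern, every value from 1.6 to 2.5 is Grade 2.

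The two repairs send the whole overlap band to opposite grades.

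**Fever**
- Celsius: Grade 3 is 39.6 to 40.5 and Grade 4 is above 40. The overlap is above 40.0 and up to 40.5, a width of 0.5 °C.
- Fahrenheit: Grade 3 is 103 to 105 and Grade 4 is above 105. There is no overlap.
- Conversions: 40.5 × 9/5 + 32 = 104.9 °F; 40 × 9/5 + 32 = 104.0 °F; (105 − 32) × 5/9 = 40.56 °C.
- The Celsius Grade 3 ceiling (40.5 °C, or 104.9 °F) agrees with the Fahrenheit boundary of 105 °F. The Celsius Grade 4 floor (40 °C, or 104.0 °F) does not. It is the odd one out.
- Example: 104.5 °F is (104.5 − 32) × 5/9 = 40.28 °C. By the Fahrenheit limits it is Grade 3 only. By the Celsius limits it is Grade 3 and Grade 4.

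**Smaller items in the same appendix**
- Platelets: Grade 3 ends at 49,000 and Grade 2 starts at 50,000, so 49,001–49,999/mm³ has no grade. Grade 1 ends at 99,000, so 99,001–99,999/mm³ has none either. If counts are reported in whole thousands (an assumption), no value falls in either gap.
- Bronchospasm: Grade 1 stops at 70% FEV1, and Grades 2 and 3 carry the same 25–50% band.

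**The case against.** The strongest reply is that this is a flaw in a few cells of a reproduced external scale, with little consequence. Much of that stands.

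- **Most rows work.** A reader might infer that the severity endpoint and the graded laboratory tables as a whole are undetermined. The documents do not support that: the defect concerns specific values in specific rows.
- **Laboratory grading is likely to be uniform.** Chemistry goes to central laboratories (Section 4.5.9) and is sent directly to the Sponsor (Section 7.1), so a single derivation would treat both arms alike. Section 6.5 also defers detailed methods to a Data Analysis Plan that is not among the documents and could hold a rule. Such a rule would not govern fever events graded by investigators.
- **Laboratory data are also summarized by descriptive statistics** (Section 6.5), so GGT and alkaline phosphatase are reported whatever their grade. Body temperature is summarized in the same way.
- **Reporting triggers are unaffected.** The Hy's Law criteria use ALT or AST with bilirubin or jaundice (Section 5.3.5.7). Both candidate fever grades are already 3 or higher, so the infusion-reaction threshold in Section 5.2.3 does not move.
- **AST and ALT do not settle the enzyme rows.** A reader might take them as proof that Grade 2 must start at 2.6 × ULN. Amylase, hyperbilirubinemia and creatinine support the opposite repair.
- **Bronchospasm should not be counted as a defect yet.** A reader might conclude that FEV1 between 50% and 70% has no grade. The identical text in two cells may come from reading the PDF, response to a bronchodilator partly separates those grades, and spirometry is not a scheduled assessment.

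None of this removes the overlaps. Appendix 7 is the operative scale, Table 3 does not cover listed items, and no tie rule is stated.

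**Conclusion.** The point holds for three rows. GGT and alkaline phosphatase from 1.6 to 2.5 × ULN can be Grade 1 or Grade 2. Fever above 40.0 and up to 40.5 °C can be Grade 3 or Grade 4. For these values the grade is not determined by the protocol.

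The consequence is limited to descriptive adverse event and laboratory grade tables, and efficacy is not affected. The 72% describes band width. The documents give no basis for estimating how many patients or results fall in the overlap.

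The conclusion assumes that Appendix 7 is applied as printed and that the Data Analysis Plan contains no rule. The table's own figures settle the fever correction. They do not settle which enzyme limit is wrong. The platelet gaps are trivial. This is a worthwhile clean-up of low priority.

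**What to change.** - **Fever:** make the Celsius Grade 4 limit agree with the Fahrenheit limit in the same cell (above 105 °F, about 40.5 °C).
- **GGT and alkaline phosphatase:** check both rows against the source scale and reconcile the Grade 1 and Grade 2 limits so that they do not overlap. If the source scale has the same overlap, state one rule, such as assigning the higher grade.
- **Derivation:** grade laboratory results centrally from the numeric values, with that one rule in both arms. Include a rounding convention, because adjacent bands are printed to one decimal (2.5, then 2.6).
- **Minor:** close the two platelet gaps, and check the bronchospasm FEV1 row against the source page before editing it.

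Section 5.1.1.2 refers to preliminary analyses of unblinded safety data from this study. The rule should therefore be dated and described as set after that point. It can still serve the final analysis in Section 6.

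The cost is a few appendix cells and one derivation program, with no change to visits, samples or patients.
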